## 2.2 Rationale

Given the benefit demonstrated from longer-term antiviral treatment of babies with symptomatic congenital CMV disease, and recognizing the fact that most of the disease burden of CMV-associated hearing loss is in the asymptotically infected population, we hypothesize that infants with asymptomatic congenital CMV infection who are treated with valganciclovir will have protection against hearing deterioration. The primary toxicity of valganciclovir is neutropenia; however, neutropenia rates among infants receiving valganciclovir in CASG studies were modest. Specifically, the rate of neutropenia experienced by infants treated in the recent Phase III CASG study was not higher than that seen in the untreated babies from the earlier CASG study (19% in the valganciclovir group versus 21% in the untreated group). Additionally, no long term complications from ganciclovir therapy have been identified among people who received treatment during the neonatal period on early CASG studies. Specifically, no adolescents who had been treated on a CASG study as young infants in the 1980s developed cancer or pubertal abnormalities when followed up in the 2000s. Given this safety profile, systematic evaluation of the treatment of babies with asymptomatic congenital CMV infection is justified due to the risk of hearing abnormalities that they face.

The selection of 4 months as the duration of antiviral therapy is based upon two findings in the CASG's previous studies of valganciclovir in infants with symptomatic congenital CMV disease who were treated for either six weeks or six months. First, the viral load data from the 6 week versus 6 month study demonstrated the attainment of virologic control by four months of age in the group that received only 6 weeks of antiviral therapy (decrease of whole blood viral load to the level that was seen in the group still receiving treatment) (Figure 2). Second, potential hepatic toxicity was detected after 4 months of treatment in subjects receiving six months of therapy. There was no increased risk of neutropenia among subjects receiving valganciclovir for longer than 6 weeks. Given that the risk of hearing impairment is lower in the asymptomatic congenital CMV population (that is, most babies with asymptomatic congenital CMV infection will not experience hearing loss), we have selected 4 months of treatment to maximize the likelihood of virologic control and minimize the likelihood of adverse effects of therapy (elevated transaminases).

It is critical that this trial be undertaken now. In 2013, the state of Utah passed a law that requires babies who fail their newborn hearing screen to be tested for CMV infection. Other states (Illinois, Connecticut, Tennessee, Texas, New York, and Florida among them) are

considering similar legislation in their 2015 legislative sessions. This type of “targeted screening” for congenital CMV infection will not identify the overwhelming majority of at-risk neonates, since only 25% of babies with asymptomatic congenital CMV who ultimately develop CMV-associated SNHL have hearing loss present in the first month of life (with the remaining 75% developing hearing loss in later months or the first few years of life). However, targeted screening portends universal screening for congenital CMV infection, as has recently been recommended by a Consensus Conference of leading world experts who gathered before the 5th International Congenital CMV Conference in Brisbane, Australia, on April 19, 2015. A similar staged implementation was seen in the 1990s with hearing screening, whereby testing newborns for hearing abnormalities began in a targeted fashion and only later expanded to universal hearing screening for all babies born in the United States. Once asymptomatic babies are identified through targeted or universal screening programs, there will be tremendous pressure on the managing physician to “do something,” which inevitably will mean treating with oral valganciclovir. Therefore, the window of time to assess the benefit, if any, versus the risk in the asymptotically infected congenital CMV population is narrow. Failure to establish the estimates of clinical effectiveness and to define the risks from treatment now could lead to widespread treatment outside of the confines of a clinical trial, thereby putting babies treated in such a manner at risk of harm with no opportunity to assess for evidence of benefit.

## 2.3 Potential Risks and Benefits

### 2.3.1 Potential Risks

The dose of oral valganciclovir to be used in this trial will be 16 mg/kg/dose administered twice daily. This is the dose evaluated in previous CASG studies of symptomatic congenital CMV disease for as well as safety, pharmacokinetics/pharmacodynamics, and efficacy. The primary clinical toxicity of valganciclovir, which is metabolized to ganciclovir, at this dose in this population is neutropenia. In the CASG’s Phase III randomized controlled study of 6 weeks of parenteral ganciclovir versus no treatment in babies with symptomatic congenital CMV disease, 63% of treated neonates developed Grade 3 or 4 neutropenia utilizing the Division of AIDS Toxicity Tables during the six week course of treatment, compared with 21% of the subjects randomized to no treatment. In the CASG study of the pharmacokinetics of oral valganciclovir, neonatal subjects received approximately two weeks of parenteral ganciclovir and four weeks of oral valganciclovir, and 38% developed Grade 3 or 4 neutropenia. In the recently published CASG study of six weeks versus six months of oral valganciclovir in babies with symptomatic congenital CMV disease, 19% developed Grade 3 or 4 neutropenia during the first six weeks of treatment during which all babies received active therapy, which is comparable to the 21% of babies in the no treatment arm of the original study. This difference in rates of neutropenia with intravenous ganciclovir and oral valganciclovir likely relates to the higher maximum concentration of the drug associated with intravenous versus oral drug delivery, and suggests that administration of the oral prodrug (valganciclovir) is a safer way to administer ganciclovir into the body than intravenous ganciclovir. Subjects treated with oral valganciclovir from week six to month six were not more likely to have neutropenia compared with those receiving placebo (21% versus 27%, respectively;  $p=0.64$ ). Thus, neutropenia induced by oral valganciclovir occurs much less frequently than with parenteral ganciclovir, and

---

appears to be limited to the first six weeks of therapy. Among subjects receiving six months of therapy with oral valganciclovir in the recent CASG study of longer-term treatment in babies with symptomatic congenital CMV disease, there was a suggestion of elevation in transaminases after four months of therapy, although this did not reach statistical significance. All laboratory abnormalities associated with valganciclovir (neutropenia and possibly transaminitis) were fully reversible upon temporary cessation of the drug.

In addition to neutropenia, the clinical hematologic toxicities of valganciclovir include anemia, thrombocytopenia, pancytopenia, and aplastic anemia. In animal studies, ganciclovir was carcinogenic, mutagenic, and caused aspermatogenesis. However, no long-term complications from ganciclovir therapy have been identified among people who received treatment during the neonatal period on early CASG studies. Specifically, no adolescents who had been treated on a CASG study as young infants in the 1980s developed cancer or pubertal abnormalities when followed up in the 2000s. Some additional adverse events reported in the valganciclovir package insert are diarrhea, vomiting, hypertension, upper respiratory tract infection, urinary tract infection, pyrexia, and headache.

Subjects will be asked to provide personal health information (PHI). All attempts will be made to keep this PHI confidential within the limits of the law. However, there is a chance that unauthorized persons will see the subjects' PHI. All records will be kept in a locked file cabinet or maintained in a locked room at the participating CASG sites. Electronic files will be password protected. Only people who are involved in the conduct, oversight, monitoring, or auditing of this study will be allowed access to the PHI that is collected. Any publications from this study will not use information that will identify subjects by name. Organizations that may inspect and/or copy research records maintained at the participating CASG sites for quality assurance and data analysis include groups such as National Institute of Allergy and Infectious Diseases (NIAID) and their authorized representatives, the Food and Drug Administration (FDA), and the study's pharmaceutical collaborator Genentech, Inc. (which would only occur with the consent of NIAID as the holder of the IND for the study).

### **2.3.2 Known Potential Benefits**

There may be no direct benefit from the experimental treatment to the asymptotically infected subjects enrolled in this study. However, six weeks of intravenous ganciclovir has been proven to protect against hearing deterioration in patients with symptomatic congenital CMV disease when treatment was initiated during the first month of life. Six months of oral valganciclovir has been proven to provide enhanced protection against hearing deterioration in this population when compared with six weeks of treatment, and to improve neurodevelopmental outcomes. This trial will determine whether prolonged oral valganciclovir therapy can protect against hearing deterioration in infants congenitally infected with CMV who are asymptomatic at birth. Subjects who participate will contribute to the knowledge about the safety and effectiveness of valganciclovir in congenitally CMV infected neonates.

---

## 3 OBJECTIVES

### 3.1 Study Objectives

Primary:

- To estimate the proportion of subjects with asymptomatic congenital CMV infection who, following treatment with 4 months of oral valganciclovir, develop sensorineural hearing loss (SNHL) by 6 months of life.

Secondary:

- To define the safety and tolerability of valganciclovir in enrolled subjects.
- To estimate the proportion of subjects with asymptomatic congenital CMV infection who, following treatment with 4 months of oral valganciclovir, develop SNHL over the first 18 months of life.

Exploratory:

- To compare changes in whole blood CMV viral load versus plasma CMV viral load during and following antiviral treatment.
- To assess correlation between CMV viral load, by body compartment, and SNHL.
- To assess correlation between development of ganciclovir resistance, by body compartment, and SNHL.
- To assess development of resistance to ganciclovir in the compartment-specific sites of blood, urine, and saliva over time.

### 3.2 Study Outcome Measures

#### 3.2.1 Primary Outcome Measures

- The number of subjects developing sensorineural hearing loss in at least one ear between Baseline and Study Month 6 [both ears with normal hearing at baseline, then at least one ear with sensorineural hearing loss (SNHL) at the 6 month follow-up]

#### 3.2.2 Secondary Outcome Measures

- Cumulative incidence of Grade 3 or higher unsolicited adverse events, safety laboratory adverse events, or serious adverse events
- Cumulative incidence of absolute neutrophil counts below 500/mm^3
- Cumulative incidence of transaminase elevation during treatment  $\geq 2$ -times the baseline value
- Cumulative incidence of adverse events leading to permanent discontinuation of valganciclovir therapy, or any adverse event that is not recovered / not resolved

- 
- Cumulative incidence of sensorineural hearing loss in at least one ear between Baseline and Study Month 4 [both ears with normal hearing at baseline, then at least one ear with sensorineural hearing loss (SNHL) at the 4 month follow-up]
  - Cumulative incidence of sensorineural hearing loss in at least one ear between Baseline and Study Month 12 [both ears with normal hearing at baseline, then at least one ear with sensorineural hearing loss (SNHL) at the 12 month follow-up]
  - Cumulative incidence of sensorineural hearing loss in at least one ear between Baseline and Study Month 18 [both ears with normal hearing at baseline, then at least one ear with sensorineural hearing loss (SNHL) at the 18 month follow-up]
  - Cumulative incidence of each degree of worsened hearing (mild, moderate, severe, profound) at Study Months 4, 6, 12, and 18, represented by the ear that has the larger degree of worsening
  - Proportion of ears of each degree of worsened hearing (mild, moderate, severe, profound) at Study Months 4, 6, 12, and 18

### **3.2.3 Exploratory Outcome Measures**

- Change in whole blood and plasma CMV viral load through Study Month 6
- Correlation of change in whole blood and plasma CMV viral load with change in hearing at Study Months 4, 6, 12, and 18.
- Correlation of change in urine CMV viral load with change in hearing at Study Months 4, 6, 12, and 18.
- Correlation of development of ganciclovir resistance in differing body compartments (blood, urine, saliva) with change in hearing at Study Months 4, 6, 12, and 18.
- Emergence and kinetics of ganciclovir resistance in differing body compartments (blood, urine, saliva) during antiviral therapy (Study Month 4), and following cessation of antiviral treatment (Study Months 5 and 6)

---

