In the analysis adjusted for CNS involvement at baseline, participants randomly assigned to receive 6 months of valganciclovir, as compared with those randomly assigned to 6 weeks of treatment, had higher Bayley-III language-composite scores at 24 months ( $P = 0.005$ ) and higher receptive-communication scale scores at 24 months ( $P = 0.003$ ). No significant interaction effects were found when outcome and CNS involvement at baseline were incorporated in a single model, indicating that the treatment benefits were similar in the group with CNS involvement and the group without CNS involvement. The differences between the 6-month group and the 6-week group with respect to Bayley-III scores were maintained when age at the initiation of treatment and prematurity were added to the model ( $P = 0.004$  and  $P = 0.003$ , respectively). All the other components of the Bayley-III assessments trended toward improved outcomes among participants in the 6-month group, as compared with those in the 6-week group.

Viral loads in whole blood decreased in parallel in the two study groups during the first 6 weeks of open-label valganciclovir therapy and then diverged after randomization (Figure 2). In the analysis that was adjusted for an interaction effect between treatment and the area under the curve (AUC) of the viral load, lower viral loads, as compared with higher viral loads, correlated with better hearing outcomes at 6, 12, and 24 months among participants in the 6-month group ( $P < 0.01$  for all comparisons) but not among those in the 6-week group ( $P > 0.68$  for all comparisons). There was no correlation between the AUC of the viral load and neurodevelopmental outcomes beyond that provided by treatment.

Figure 2. Whole blood viral load in subjects receiving 6 months (green) and 6 weeks (red) of oral valganciclovir.

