The available data on viral load levels between symptomatic and asymptomatic infants congenitally infected with CMV consistently have demonstrated that babies born with symptoms of congenital CMV disease have higher viral loads than do babies born without any symptoms of congenital CMV infection. However, while the median values are different between the two groups, there is significant overlap at the individual level such that a baby with a given viral load could be either in the symptomatic group or in the asymptomatic group. Additionally, methodologic differences (assays with different levels of detection in the published studies) make it difficult to compare data across these published results. At the current time, threshold viral load values above which a baby could reliably be categorized as having symptoms and below which they could reliably be considered to be asymptomatic are not clearly delineated.

Several studies that have included infants with both symptomatic and asymptomatic congenital CMV infection have demonstrated that higher viral loads correlate with sensorineural hearing loss (SNHL). Studies that have focused primarily or exclusively on asymptotically infected infants have reported conflicting results. Ross et al.'s 2009 publication found no correlation between a higher viral load and SNHL among asymptotically infected infants, but found that lower viral loads ( $< 3,500$  ge/mL) are associated with a lower risk of SNHL. However, Forner et al.'s recent publication found that asymptomatic infants with viral loads of  $\geq 17,000$  copies/mL were more likely to develop SNHL. The Forner paper, though, found no difference in the duration of detectable virus in the blood or urine and SNHL – in other words, subjects who did or did not develop SNHL shed virus in blood or urine for the same duration of time. Given that higher viral loads generally would take a longer period of time to decrease compared with lower viral loads, these data have some intrinsic contradictions. The Forner study

also was limited by a very small sample size – only 33 total infants, with only 10 having SNHL. Even studies by the same research group have reported conflicting results, with an earlier study that reported identifiable thresholds correlating with SNHL yielding to a later study with a larger sample size that did not find such correlation.

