### **11.4.4 Efficacy Analysis Plan**

Primary analysis:

The primary analysis is estimating the proportion of subjects with asymptomatic congenital CMV infection who, following treatment with 4 months of oral valganciclovir, develop SNHL by 6 months of life in at least one ear. Due to the small expected number of subjects who will develop SNHL by 6 months, the Clopper-Pearson method will be used to calculate an exact 95% upper confidence bound for the primary outcome.

Secondary analyses:

---

For the proportion of subjects who develop SNHL at 4, 12, and 18 months post baseline, we will also use the Clopper-Pearson method to obtain an estimate of the 95% upper confidence bounds separately for each period. In each of these hearing outcomes, we will provide a breakdown on the degree of worsening (mild, moderate, severe). This method will also be used to define safety and tolerability of valganciclovir by estimating the incidence of adverse events of interest. If there is enough information in the data collected, we will use a large-sample method for estimating the 95% confidence interval of interest over the more conservative Clopper-Pearson method.

Analysis of actual viral load will be done using log base 10 transformation for both whole blood and plasma CMV viral loads. Undetectable viral load value will be replaced by a value of 10. To investigate the change over time, we will model the log base 10 viral load using mixed model to accommodate repeated measures. The covariance structure (selected among unstructured, exchangeable, autoregressive, exponential, and toeplitz) that best describes the correlation among the repeated measures over time will be selected using the AIC model selection index. Note that there will be 13 time points for which viral load will be measured. Hence, if time will be represented as discrete variables in the model, this will require spending 12 degrees of freedom in the model, which we believe is unnecessary. In our modeling we will represent time as a continuous variable and will consider fitting linear, quadratic, and cubic to approximate non-linear trends. The simplest model with a good fit based on the test of the coefficients, as well as the profile curves, will be selected. Modeling will be done separately for whole blood and plasma viral loads.

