The same method of modeling will be employed to compare the whole blood and plasma CMV viral loads. However, the outcome will be the difference between the whole blood and plasma CMV viral load values for each subject at each time point. If the differences over time are found to be modeled by a linear function and there is no evidence to show that the slope of this line is significantly different from zero, then there is no evidence to conclude a difference between the average viral loads based on whole blood and plasma. Otherwise, there is a difference and this difference will be examined and discussed in more details based on the results of the fitted model.

We will investigate the how viral load is related to hearing outcomes using generalized linear model for binary outcome at each time point relative to baseline hearing.

All tests will use a 5% significance level, i.e., p-values<0.05 will be considered significant.

Ganciclovir resistance will be assessed by molecular methodologies (e.g., deep sequencing, Sanger sequencing, PCR). Blood, urine, and saliva specimens will be obtained serially.

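### Hearing is to be related to change in viral load with no stated adjustment for baseline load, so the association may be diluted or, if baseline load raises risk, wrong-signed.

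*Combined protocol and SAP*

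**What the plan says.** Section 3.2.3 makes change in load the biomarker: "Correlation of change in whole blood and plasma CMV viral load with change in hearing at Study Months 4, 6, 12, and 18". A parallel item covers urine. The exploratory objective in Section 3.1 speaks of viral load, not of change.

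The only analysis text is in Section 11.4.4: "We will investigate the how viral load is related to hearing outcomes using generalized linear model for binary outcome at each time point". The sentence ends by making the outcome relative to baseline hearing. That is the only baseline it mentions. It does not say whether the predictor is change, current level or a summary over time, and it names no covariate. The same section sets a 5% significance level for all tests.

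Two handling rules apply: "Analysis of actual viral load will be done using log base 10 transformation for both whole blood and plasma CMV viral loads", and "Undetectable viral load value will be replaced by a value of 10". Neither mentions urine.

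Blood for viral load is taken on Study Day 1 and at each visit to Month 6. Urine is attempted on Day 1 and at Months 4, 5 and 6 (Sections 4 and 7). No viral-load sample is scheduled at Months 12 or 18.

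Section 2.1 reports that in mixed symptomatic and asymptomatic cohorts "higher viral loads correlate with sensorineural hearing loss", but describes the results in asymptomatic infants as conflicting. In the earlier symptomatic trial the viral-load measure was an area under the curve, and in the 6-month group "lower viral loads, as compared with higher viral loads, correlated with better hearing outcomes at 6, 12, and 24 months".

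**The concern.** Every infant is treated, so an infant who starts high has further to fall. If hearing loss is regressed on the fall alone, the fall carries two things: how well the virus was suppressed, and how high the load was at birth. If high load at birth also raises the risk of SNHL, the infants with the largest falls are the ones at highest risk, and effective suppression can look harmful. If load at birth carries no risk of its own, a real benefit of lower on-treatment load is still pulled towards no association.

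There is no control arm, so this is one of the few places where the trial's own data speak to whether virologic response tracks hearing. A misleading sign, reported against a 5% threshold, could be taken up in later work.

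**Working it through.** The plan states no figure for this analysis, so there is none to reproduce. The check is algebra plus simulation. Every viral-load input below is an assumption; the documents give none.

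**1. A fall carries baseline information.** An undetectable value is set to 10, which is 1 on the log10 scale. An infant who becomes undetectable therefore has a fall of log10(baseline) − 1. To illustrate with the two thresholds in Section 2.1 (different assays, so for scale only): from 17,000 the fall is 4.23 − 1 = 3.23, and from 3,500 it is 3.54 − 1 = 2.54. Both infants end at the same level; the difference of 0.69 is all baseline.

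**2. Model.** Let B be baseline and F on-treatment log10 load, with fall D = B − F. Suppose logit(SNHL) = a + bB + cF. Substituting F = B − D gives a + (b + c)B − cD. Once B is in the model, change and level carry the same information: the odds ratio per log10 fall is exp(−c), the inverse of that per log10 level.

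**3. Leaving B out.** Assume B has SD 1 (mean 3.0 to 3.5) and F = 0.3B + 0.9 + e, with the SD s of e from 0.3 to 0.8. Ignoring the floor:
- var(D) = 0.49 + s²; cov(B, D) = 0.7; cov(F, D) = 0.21 − s²
- unadjusted log odds ratio per log10 fall ≈ [0.7b + c(0.21 − s²)] / (0.49 + s²)

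Take c = ln 1.5 = 0.405, so the true odds ratio per log10 fall is 1/1.5 = 0.67. With a baseline odds ratio of 2, b = 0.693 and 0.7b = 0.485:
- s = 0.3: (0.485 + 0.405 × 0.12)/0.58 = 0.92, odds ratio 2.51
- s = 0.8: (0.485 − 0.405 × 0.43)/1.13 = 0.275, odds ratio 1.32

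**4. Simulation with the floor at 1** (300,000 infants, 3.18% event rate). The correlation of fall with baseline is 0.72 to 0.92, and 1% to 17% of values are at the floor.

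| Baseline odds ratio per log10 | Formula, s = 0.3 / 0.8 | Simulated, unadjusted |
|---|---|---|
| 1 | 1.09 / 0.86 | 0.87 to 1.09 |
| 1.25 | 1.42 / 0.98 | 1.02 to 1.45 |
| 1.5 | 1.77 / 1.10 | 1.16 to 1.76 |
| 2 | 2.51 / 1.32 | 1.38 to 2.49 |
| 3 | 4.10 / 1.69 | 1.79 to 3.97 |

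With B in the model, the simulated odds ratio is 0.63 to 0.68 for baseline odds ratios of 1, 2 and 3.

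**5. At the trial's size.** Expected events are 176 × 0.0318 = 5.6, or 176 × 0.10 = 17.6 at the 10% rate in Section 2.1. A second set of inputs was used: B mean 3.5, SD 1; slope 0.3; residual SD 0.7; 74% or 9% undetectable; two-sided 5% test. The table gives the percentage of simulated trials showing significant harm from larger falls, without adjustment.

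| Baseline odds ratio | Effect of a log10 fall | 3.18% rate | 10% rate |
|---|---|---|---|
| 2 | none | 21 to 34% | 45 to 70% |
| 2 | halves the odds | 8 to 25% | 23 to 66% |
| 1 | none, or odds cut to a half or a third | 0 to 4% | 0 to 3% |

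With baseline load added, false harm is 0 to 2% in all of these.

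**6. Level alone is not a safe substitute.** With no suppression effect and a baseline odds ratio of 2, hearing regressed on unadjusted on-treatment level gives an odds ratio of 1.3 to 3.2 per log10. That is a false finding in the flattering direction.

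**The case against.** The strongest reply is that the plan does not commit itself to an unadjusted change analysis. A reader might infer that it does. The documents do not support that: Sections 3.1 and 11.4.4 speak of load, only the outcome list in Section 3.2.3 says change, and no covariate is ruled out. The gap is one of silence. It still matters, because the listed outcome taken literally is the unadjusted one, and the choice stays open until the data are seen.

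A reader might also infer that suppression will look harmful in this trial. That needs baseline load to predict SNHL. In asymptomatic infants Section 2.1 reports one study with no correlation for higher loads but lower risk below 3,500 ge/mL, and one of only 33 infants with more SNHL at 17,000 copies/mL or above. If there is no baseline effect, the usual result is dilution, with little or no reversal.

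Nor can one say that most on-treatment values will sit at the floor. The documents give no undetectable rate, and the bias in step 4 arises with few values there.

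Imprecision is a fair objection. With about 6 events, the correctly adjusted estimate (truth 0.67) still fell on the wrong side of 1 in 24% to 41% of simulated trials. When about 75% were undetectable, fall and baseline were nearly collinear, and the median adjusted odds ratio reached 2.79 with a truth of 1. Adjustment removes the systematic error, not the noise. That argues for cautious reporting, not for leaving baseline out.

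Finally, the outcome is exploratory, no decision hangs on it, and it is not the only internal evidence: correlations of resistance with hearing are planned too.

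**Conclusion.** The concern holds as a gap in specification. An association of hearing with unadjusted change in viral load would not isolate virologic response. Under the assumed inputs, a true odds ratio of 0.67 per log10 fall appears as about 0.9 to 1.1 when baseline load has no effect on SNHL, and as 1.4 to 4.0 when the baseline odds ratio is 2 to 3. Including baseline load restores 0.63 to 0.68.

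The direction of the problem rests on the coupling of fall and baseline, which is close to arithmetic. Its size, and whether the sign reverses, rest on assumed load distributions and on a baseline effect that the documents leave unsettled. The primary estimate of SNHL by 6 months is not touched.

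**What to change.** In Sections 3.2.3 and 11.4.4:

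- Include baseline log10 load as a covariate in every model of hearing on viral load. Name the predictor in advance: change or on-treatment level (equivalent once baseline is in the model), or time-averaged log10 load.
- Use only samples dated on or before the hearing test. For the Month 12 and 18 tests the series ends at Month 6, when sampling stops.
- For urine, use baseline and Month 4 for the Month 4 test, and baseline with Months 4 to 6 for later tests. State the scale and the rule for undetectable values for urine as well.
- Fit a penalised (Firth) or exact logistic model.
- Where events are too few for two terms, present the data descriptively by baseline load. Do not interpret either unadjusted change or unadjusted on-treatment level as evidence on virologic response.

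The cost is wording: the Day 1 load is already scheduled, and no visit or sample is added. The price in the results is wide intervals, and near-collinearity if most infants become undetectable, which the report should state.
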